2.1 Primary objective(s)

Primary objective(s)	Endpoints related to primary objective(s)	
To assess the efficacy of multiple i.a. injections of LNA043 in regenerating the articular cartilage tissue	Articular cartilage bi-layer collagen organization evaluated with T2 relaxation times measured in superficial and deep layers by T2 mapping Magnetic Resonance Imaging (MRI) at Week 16 and 28 (Part A)	
	• Change in cartilage volume/thickness in the index region at Week 28 and 52 (Part B)	
To assess safety and local tolerability of multiple i.a. injections of LNA043	Systemic and local Adverse Events Electrocardiograms (ECGs) Vital signs Hematology, blood chemistry, urinalysis	

2.2 Secondary objective(s)

Secondary objective(s)	Endpoints related to secondary objective(s)		
To assess the extent of the repair cartilage tissue following multiple i.a. injections of LNA043	 Change in volume of cartilage defect filling evaluated with MRI at Week 16 and 28 (Part A) Articular cartilage bi-layer collagen organization evaluated with T2 relaxation times measured in superficial and deep layers by T2 mapping Magnetic Resonance Imaging (MRI) at Week 28 and 52 (Part B) 		
To evaluate systemic and local PK of LNA043 following multiple i.a. injections of LNA043	Serum and synovial fluid PK profile of LNA043 and ANGPTL3		
To assess the potential immunogenicity of LNA043	Presence and characterization of anti- LNA043 antibodies in serum at Day 1, Day 15, Day 50, Day 106 and Day 190 (Part A) and Day 1, Day 29, Day 57, Day 85, Day 113, Day 197 and Day 365 (Part B)		

2.3 Exploratory objective(s)

3 Investigational plan

3.1 Study design

3.1.1 Part A

This is a non-confirmatory, randomized, placebo-controlled, patient and investigator blinded study in patients with a partial thickness cartilage lesion of the knee.

Commercially Confidential Information

Following their informed consent, patients will be assessed for eligibility at the screening visit. Whenever possible, the MRI should be performed in advance, or immediately after eligibility assessment on the same day of screening within the screening period (Day -35/-5). Safety laboratory assessments should be performed as close as possible to dosing Day 1.

Investigators may perform an unscheduled visit between Screening and first treatment on Day 1 if deemed to confirm eligibility of the subject, or verify safety.

On Day 1, eligible patients will receive either an i.a. injection of LNA043 (20 mg CCI or matching placebo (CCI) according to a 3:1 randomization ratio. CCI

At each treatment visit, safety and pharmacokinetics will be assessed as detailed in the Assessment schedule (Table 8-1). The investigator will schedule telephone calls with the patient approximately 48 hours after each study drug administration, and two weeks after the last injection, for follow-up assessment of safety. In case of safety concerns, the patient will return to the hospital for assessment and follow-up.

Commercially Confidential Information

The EOS visit assessments should be performed also in case of premature patient discontinuation for any reason (except in case of consent withdrawal).

3.1.2 Part B

This is a non-confirmatory, randomized, placebo-controlled, patient and investigator blinded study in patients with K&L 2-3 knee OA.

Commercially Confidential Information

Following their informed consent, patients will be assessed for eligibility at the screening visit. Investigators may perform an unscheduled visit between Screening and first treatment on Day 1 if deemed to confirm eligibility of the subject, or verify safety.

Screening X-ray will be evaluated by the central reader for eligibility. Baseline MRI will be performed after eligibility has been verified. On Day 1, eligible patients will receive a CCI i.a. injection of either LNA043 20 mg, LNA043 40 mg, or matching placebo according to a 1:1:1 randomization ratio. Commercially Confidential Information

During the treatment period, safety and pharmacokinetics will be assessed as detailed in the Assessment schedule (Table 8-2). Patients will be monitored on site 3 hours after the i.a. injections. The investigator will schedule telephone calls with the patient approximately 48 hours after each study drug administration for follow-up assessment of safety. In case of safety concerns, the patient will return to the clinical site for assessment and follow-up.

3.2 Rationale of study design

The design of this study addresses the primary objective of cartilage healing in patients with articular cartilage defects of the knee and knee OA and takes into account (i) the clinical need; (ii) clinical and preclinical data on LNA043; (iii) current practice with intra-articular injectable drugs; and (iv) the burden on patients with articular cartilage lesions and knee OA. The combination of MRI with cartilage-specific pulse sequences (Juras et al 2016a)

Commercially Confidential Information will ensure appropriate evaluation of LNA043 effect, from both a morphological and a functional standpoint.

The study has been designed as patient and investigator blinded in order to ensure that be investigators and patients remain in a state of equipoise, so that a putative difference betwen the treated and control groups can be interpreted as an effect of study treatment. To evalue e potential unconscious bias at the patient level, patients will be asked at EoS, which treatment they believe they have received. Since the assessment of the envisioned endpoints is independent of the investigator, a comparable evaluation at the investigator level is not planned.

3.2.1 Part A

- Randomization will be 3:1 (treatment:placebo), in order to reduce the number of people exposed to placebo, who will not have the chance for therapeutic benefit.
- Regarding the patient population, both lesions to the patella and to the femoral
 condyles/trochlea will be addressed. This will allow us to examine LNA043's effect in these
 two patient groups, characterized by different clinical, morphological and biomechanical
 features, and by a differential response to surgical procedures (Filardo et al 2014), in order
 to better inform further development of LNA043. Accordingly, randomization will be
 stratified by type of lesion (femoral condyle/trochlea or patella).

Commercially Confidential Information

- A follow-up period at Week 52 (48 weeks after the last study dose) is considered adequate to evaluate cartilage healing and to better understand the kinetics of cartilage growth, durability of the regenerated tissue and long-term efficacy in this population. (Le Graverand-Gastineau 2010, Raynauld et al 2004)
- Inclusion criteria (*e.g.*, BMI<33, age range 18-55 years), and a limited range of lesion depth (partial thickness lesions), corresponding to grade II-IIIA according to the International Cartilage repair Society (ICRS) classification) (Brittberg and Winalski 2003), have been selected in order to ensure homogeneity in a small patient sample.

3.2.2 Part B

- Based on the positive results of the CLNA043X2201 study and of this ongoing CLNA043X2202 study (Part A), a broader patient population of knee OA with high medical need patient population is now being evaluated in part B.
- The patient population of knee OA K&L 2-3 with JSW 2.00-4.00mm has been selected based on the post-hoc analysis of the FORWARD trial (Gühring et al 2019),

- The MRI data collected at different time points will allow for the evaluation of the short-and long-term effect of one monthly cycle of i.a. treatment with LNA043 and a comparison between the 2 doses tested (20 mg and 40 mg). Meanwhile, since the image analysis will cover well-defined regions the articular cartilage throughout the knee as has been done in part A, results from part B, especially those obtained from the 20 mg group, may also be compared with the results from part A to evaluate the potential added benefit of the monthly dosing regimen in the index region (as defined in part B) vs the damaged region (as defined in part A).
- The monthly dosing regimen (x 4) has been selected based on the results of the FIH clinical study, which suggests a long PD effect of LNA043.

3.3 Rationale for dose/regimen, route of administration and duration of treatment

3.3.1 Part A

The dose of LNA043 given in this study will be 20 mg, by i.a. injection

Commercially Confidential Information

In conclusion, clinical experience to date with LNA043 indicates that this compound is safe and well-tolerated. A dose of 20 mg has been selected for repeat dosing, once weekly for four weeks, based on safety and feasibility, and in order to maximize the likelihood of delivering a sustained, pharmacodynamic effect on cartilage repair in the knee. Moreover, the proposed dose regimen is also consistent with current non-operative practices for the symptomatic treatment of cartilage lesions, including *e.g.*, i.a. hyaluronan injections which are administered up to five times once-weekly.

3.3.2 Part B

Part B of this study aims to assess a potential incremental treatment benefit of 20 mg/knee vs 40 mg/knee dose CCI Based on the available clinical data, the 40 mg/dose in Commercially Confidential Information , might have favorable risk-benefit profile compared to the single and repeated weekly dosing regimens tested up to date.

The proposed dosing regimen takes into account that:

- LNA043 displayed a favorable safety profile with no significant drug related safety signals, up to the maximum evaluated dose of 40 mg/lenee in the FIH SAD study.
- Commercially Confidential Information

- Up to date understanding of dose-response characteristics of LNA043 in the targeted population is limited. However, dose dependency of PD responses in the FIH SAD study indicate that the 40 mg/lenee dose may be associated with an incremental treatment benefit without major safety and tolerability concerns.
- Importantly, the PD results from FIH SAD, showed upregulation of chondrogenic genes for up to 21 days, indicating lasting effects and monthly dosing regimen seem to be more appropriate to fully elicit potential treatment benefit of LNA043.

In summary, the less frequent, once-monthly administration of LNA043 up to 40 mg/lenee is not expected to be associated with an increased safety/tolerability risk but potentially lead to an incremental treatment benefit for treated patients. Importantly, Part B of the study provides essential information for further optimization of the dosing regimen.

3.4 Rationale for choice of comparator

No cartilage-anabolic compound able to promote cartilage healing has been approved so far. Therefore, the comparator will be placebo.

Placebo contains the same formulation and excipients as the investigational drug, without the active agent. Additionally, the study will be performed with identical standard of care procedures in both the control and investigational drug arms.

3.5 Purpose and timing of interim analyses/design adaptations

Commercially Confidential Information

3.6 Risks and benefits

It is not known whether there will be a benefit for the patients participating in this study. However, data from the completed and ongoing studies demonstrate a cartilage anabolic activity of LNA043, with the potential to regenerate the articular cartilage of the knee. No disease modifying therapy exists as standard of care for patients with articular cartilage damage, including from osteoarthritis. Therefore, no such therapies will be withheld by joining this study. The risk to patients in this trial will be minimized by adherence to the eligibility criteria, close clinical monitoring, and stopping rules.

Invasive, study-specific procedures include synovial fluid aspiration and i.a. injection of LNA043: as with any intra-articular injection, a risk of iatrogenic infection exists. Recent reports found infection rates following i.a. injection of steroids between 1 in 3000 and 1 in 50,000 (Lavelle et al 2007). However, few orthopedists and rheumatologists have encountered a case of poststeroid septic arthritis (Charalambous et al 2003). In addition, when proper technique is applied in a healthy population, and when a non-steroidal drug is used, this rate is supposed to be considerably lower.

Sterile technique will be used in all phases of drug reconstitution and administration to further reduce the risk of infection. Potential adverse effects may include local reactions at the site of injection, such as local pain, swelling or inflammation. Potential adverse events will be monitored clinically. Synovial fluid aspiration will be performed at the same time as the i.a. injection of LNA043, with no additional harm or discomfort for the patient. Systemic concentrations following i.a. administration to the patients studied in the FIH study remained <300 ng/mL and within the physiologic range for circulating concentrations of ANGPTL3. In addition, based on the current data available, LNA043 is not expected to persistently bind to or block its receptors.

Being a modified protein, hypersensitivity and/or immunogenicity to LNA043 may occur.

Commercially Confidential Information

In the completed and ongoing clinical studies, no case of local or systemic hypersensitivity reactions have been observed, and no patient developed ADA after a single or multiple intraarticular injection of LNA043. The impact of neutralizing antibodies that may cross-react with
endogenous ANGPTL3 is not known, but the likely impact is considered relatively low.
Humans with loss-of-function variants in both copies of the ANGPTL3 gene have low plasma
LDL-C, low HDL-C, and low triglycerides, but no obvious adverse consequences, suggesting
that absence of ANGPTL3 does not result in any serious effects. Development of anti-LNA043
antibodies will be monitored, as well as any potential reactions related to such antibodies, such
as antibody-mediated arthropathy or impact on lipid metabolism or renal function, will be
monitored closely with the corresponding safety plan in place.

Based on a comprehensive analysis of all safety data from both completed and ongoing preclinical and clinical studies, there is no evidence to suggest that treatment with LNA043 increases the risk of hypersensitivity in humans.

Commercially Confidential Information

In order to mitigate this risk in humans, patients with a history of hypersensitivity reactions to any of the study treatments or excipients or to drugs of similar chemical classes will be excluded from participation in this study. Study drug administration will be administered at locations with emergency care facilities, and patients are required to undergo observation for three hours post-injection prior to leaving the site, to ensure their safety. Patients who experience any Grade hypersensitivity reaction must not be re-dosed.

Women of child bearing potential will be informed that taking the investigational drug may involve unknown risks to the fetus if a pregnancy was to occur during the study, and agree that in order to participate in the study they must adhere to the contraception requirement for the duration of the study. If there is any question that the subject will not reliably comply, they should not be entered in the study.

Risks of imaging procedures

For screening purposes, a standing long leg view of the lower limbs and a Merchant view of the patello-femoral joint are required. These are often performed during the routine evaluation of patients with knee pain, but not always. Consequently, in some patients they will be obtained only for research purposes. The total amount of radiation exposure per subject from these X-rays will be about $100 \, \mu Sv$. This amount of radiation is equivalent to approximately

13.8 days of background exposure (approx. 0.3 μSv per hour at sea level). For effective radiation doses under 3 mSv (300 mrem), the risk is considered to be "minimal". Therefore, the radiation exposure in this study involves minimal risk and is necessary to ensure eligibility of patients.

The only imaging technique used in this study for follow-up purposes is MRI. MRI is a non-invasive radiology technique that has no x-ray radiation exposure. No MRI contrast agent will be administered in this study. Thus in principle, MRI scans can be repeated in the same patient as often as necessary. The MRI scanning equipment may cause a feeling of claustrophobia in susceptible persons. The presence of metal in the body may also be a safety hazard or affect a MRI image quality. For more information, see exclusion criterion 11.

There may be unknown risks of LNA043 which may be serious.

Covid-19 risk assessment

Novartis is committed to supporting the safety and well-being of our study participants, investigators, and site staff. All local regulations and site requirements should be applied in the countries that are affected by the COVID-19 pandemic. The Novartis clinical trial team will review the situation in each participating country and work with Investigators to continue to ensure the safety of participants during the conduct of the trial.

A benefit/risk assessment has been made and has been determined to not significantly change for the participants that are planned to be enrolled in the proposed clinical trial. As the COVID-19 situation evolves, Investigators must use their best judgement to minimize risk to participants during the conduct of the study.

3.6.1 **Blood sample volumes**

A maximum of 227 mL of blood is planned to be collected in each part over a period of up to 61 weeks, from each subject as part of the study. Samples for monitoring of any safety findings would be in addition to this. This is not considered to be a risk for this population.

Timings of blood sample collection are outlined in the Assessment Schedule, Table 8-1 and Table 8-2.

A summary blood log is provided in the Site Operations Manual, together with instructions for all sample collection, processing, storage and shipment information.

See Section 8.9 regarding the potential use of residual samples.

4 **Population**

Part A

In Part A, the study population will be comprised of male and female patients with partial thickness cartilage lesions of one knee. A total of approximately 60 patients will be enrolled in the study and randomized. Randomization will be stratified by type of lesion (femoral condyle or patella). At least 48 patients are expected to complete the study (20% drop out rate). Additional patients may be enrolled if the dropout rate will exceed 20%.

The investigator must ensure that all patients included in the study meet the eligibility criteria. No additional criteria should be applied by the investigator, in order that the study population will be representative of all eligible patients. Patient selection is to be established by checking through all eligibility criteria at screening and before dosing. A relevant record (e.g. checklist) of the eligibility criteria must be stored with the source documentation at the study site.

Deviation from any entry criterion excludes a patient from enrollment into the study.

Commercially Confidential Information

Part B

In Part B, the study population will be comprised of male and female patients with knee OA (K&L 2-3). A total of approximately 75 patients will be enrolled in the study and randomized. At least 69 patients are expected to complete the study (10% drop out rate). Additional patients may be enrolled if the dropout rate will exceed 10%. The investigator must ensure that all patients included in the study meet the eligibility criteria. No additional criteria should be applied by the investigator, in order that the study population will be representative of all eligible patients. Patient selection is to be established by checking through all eligibility criteria at screening and before dosing. A relevant record (e.g. checklist) of the eligibility criteria must be stored with the source documentation at the study site.

In total, 135 patients are expected to be randomized into the study.

Deviation from any entry criterion excludes a patient from enrollment into the study.

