	Part B ONLY: History of knee replacement in either knee		
	Part B ONLY: Presence of severe hip OA conditioning lower limb function		
	Part B ONLY: Nephrotic syndrome and/or significant proteinuria		
	 Part B ONLY: History of coagulopathy or medical condition requiring anticoagulation which would preclude knee injection (antiplatelet or anticoagulant treatment [for patients using warfarin, INR to be <3 prior to injection], is allowed) 		
Study treatment	tudy treatment Part A:		
Ctudy additions	• Single i.a. injection of 20 mg [LNA043],	CCI	
	• Single i.a. injection of placebo to 20 mg [LNA043],	CCI	
	Part B:		
	• Single i.a. injection of 40 mg [LNA043],	CCI	
	• Single i.a. injection of 20 mg [LNA043],	CCI	
	Single i.a. injection of placebo,	CCI	
Efficacy/PD	Part A:		
assessments	 Articular cartilage bi-layer collagen organization eva T2 relaxation times measured in superficial and dee T2 mapping MRI 		
	Part B:		
	Change in volume of cartilage defect filling evaluated with MRI		
Key safety	Adverse event monitoring		
assessments	 3 hours observation period post every i.a. LNA043 a Physical examination	administration	
	Monitoring of laboratory markers in blood and urine		
Other assessments	Commercially Confidential Information		
Data analysis	The primary efficacy variable in Part A articular cartil	age hi laver collages	
Data allalysis	The primary efficacy variable in Part A, articular cartilage bi-layer collagen organization, assessed based on MRI at Week 16 and 28, and the primary efficacy variable in Part B, change from baseline in volume of cartilage defect filling evaluated with MRI at Weeks 28 and 52, will be analyzed using a mixed model with repeated measures (MMRM), including baseline and both time points to compare treatment groups at Week 16 and Week 28		
Key words	Articular cartilage, partial thickness cartilage lesion, knee, ca	artilage regeneration	

1 Introduction

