6.9 Recommended treatment of adverse events

Treatment of AEs should be in line with the Investigational site procedures.

From the completed and ongoing clinical trials, no case of local or systemic hypersensitivity reactions have been observed with LNA043 to date. Due to the potential risk of serious allergic reactions, immediate access to full resuscitation equipment and drugs must be available, including adrenaline for injection and staff trained in the use thereof (i.e. at locations with emergency care facilities). If symptoms of a systemic reaction, such as urticaria, angioedema or severe asthma occur, symptomatic treatment should be initiated immediately according to local treatment protocols. Study participants in Part A will be monitored at the clinical site for at least 1 (one) hour post intra-articular injection or longer at the discretion of the Investigator to ensure adequate safety monitoring. Study participants in Part B are required to undergo observation for three hours post-injection prior to leaving the site. Patients who experience any Grade hypersensitivity reaction in Part B must not be re-dosed.

Medication used to treat AEs must be recorded on the Concomitant medications/Significant non-drug therapies CRF.

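### For Part A, the protocol gives two different post-injection observation times and two different scopes for the no-re-dosing rule after a hypersensitivity reaction

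*Protocol*

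**What the plan says.** Three places in the protocol deal with one or both of these safeguards in terms that reach Part A.

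- **Section 3.6 (Risks and benefits).** On observation: "patients are required to undergo observation for three hours post-injection prior to leaving the site, to ensure their safety". On re-dosing: "Patients who experience any Grade hypersensitivity reaction must not be re-dosed". Neither sentence names a part.
- **Synopsis, key safety assessments.** It lists "3 hours observation period post every i.a. LNA043" administration, again with no part named and with nothing on re-dosing.
- **Section 6.9 (Recommended treatment of adverse events).** This section separates the parts. For Part A: "Study participants in Part A will be monitored at the clinical site for at least 1 (one) hour post intra-articular injection or longer", the extension being left to the investigator. For Part B: "Study participants in Part B are required to undergo observation for three hours post-injection prior to leaving the site". On re-dosing: "Patients who experience any Grade hypersensitivity reaction in Part B must not be re-dosed".

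Section 3.1.2 also gives three hours for Part B. The visible text of Section 3.1.1 gives no on-site observation time for Part A.

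**The concern.** Observation after injection and the bar on re-dosing are two of the measures that Section 3.6 offers against hypersensitivity. Section 6.9 is the section a site would open when handling such a reaction, and it does not carry either measure into Part A in the same form. Part A patients receive 20 mg or placebo once weekly for four weeks (Section 3.3.1; SAP Section 1.4.1), so whether to give the next injection after a reaction is a decision that can actually arise.

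The stakes are practical. The same conduct can comply with one section and deviate from another. Section 10.3 requires protocol deviations to be determined, and monitors working from different sections could classify an early release or a further injection differently. A reader of the report also could not tell from this protocol which observation period lies behind the Part A hypersensitivity data.

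**Working it through.** No sample size, power or error rate is involved, so the check is a comparison of the texts.

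| Rule | Synopsis | Section 3.6 | Section 3.1.2 | Section 6.9 |
|---|---|---|---|---|
| Observation, Part A | 3 h (no part named) | 3 h, required (no part named) | not applicable | at least 1 h |
| Observation, Part B | 3 h (no part named) | 3 h, required (no part named) | 3 h | 3 h, required |
| No re-dosing, Part A | not addressed | applies (no part named) | not applicable | not stated |
| No re-dosing, Part B | not addressed | applies (no part named) | not addressed | applies |

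**Part B.** Every statement agrees.

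**Part A.** The minimum observation time is 3 h in two places and 1 h in a third, a difference of 3 − 1 = 2 h per injection. The bar on re-dosing is present in 3.6 and absent from 6.9.

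**Can Section 3.6 be read as Part B only?** Its wording does not support that.
- Its opening paragraph concerns the whole trial: "The risk to patients in this trial will be minimized by adherence to the eligibility criteria, close clinical monitoring, and stopping rules".
- It discusses a patello-femoral X-ray view, and patellar lesions are an eligibility feature of Part A (Section 4.1, criterion 5).
- Elsewhere the protocol labels text that belongs to one part. Section 6.5 does so, and the synopsis row on efficacy assessments is split by part while the safety row that follows is not.

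**What each text allows.** A site that keeps to 3.6 also satisfies 6.9, because a minimum of one hour does not exclude three, and 6.9 says nothing about Part A re-dosing. The reverse fails. A site that keeps to 6.9 alone could release a Part A patient at one hour, or give the next injection after a reaction, and either act departs from 3.6.

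**How much Part A dosing is left.**
- Planned Part A enrolment: about 60 (Section 4).
- Part A patients in Table 1-1, cut-off 31-Jan-2020: 43 + 15 = 58. This protocol version reports those data, so it was written after that date.
- Patients not yet in the table: about 60 − 58 = 2. At four injections each, that is about 2 × 4 = 8 injections.
- This count assumes that the 58 had completed their injections, which the documents do not state, and that no one was added. Section 4 allows additional Part A patients if dropout exceeds 20%.

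**The case against.** The best defence is that Section 6.9 is the only visible passage that addresses both parts by name on these rules, so its split may be the intended one. Section 3.1.2 is compatible with that: three hours appears there for Part B and not in the visible Part A design text. The synopsis bullet and the benefit/risk narrative would then be general statements that were not narrowed. This may be what happened, but nothing visible says that 6.9 prevails.

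It can also be said that fuller rules may exist out of view. The body of Section 7.2, the stopping rules in Section 7.5 and Table 8-1 are not visible, and the Site Operations Manual is a separate document. They may contain a Part A rule. They would not remove the difference between 3.6 and 6.9.

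Four stronger readings are tempting, and the documents do not support them.

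- A reader might infer that sites have no way to decide what to do. That goes too far, since following 3.6 meets both sections. Section 6.9 omits a Part A re-dosing rule; it does not permit re-dosing.
- A reader might infer that the whole mitigation of hypersensitivity risk is missing from Part A. Section 3.6 also lists exclusion of patients with a history of hypersensitivity and dosing where emergency care is available. Section 6.9 requires resuscitation equipment and trained staff without limiting this to a part. None of these is in dispute.
- A reader might multiply the two-hour gap by every planned Part A injection. That is only a ceiling: most of those injections were probably given before this version, and the text that governed them is not visible.
- A reader might infer that reactions were missed and that support for Part B dosing is weakened. Part A also has telephone calls about 48 hours after each injection (Section 3.1.1) and adverse event questioning at each visit (Section 9.1). The visible Part B dose rationale (Section 3.3.2) does not cite an absence of hypersensitivity. Variation between sites is a possibility, not something the documents show.

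**Conclusion.** The inconsistency is real and confined to Part A: a required three hours against a minimum of one hour, and a bar on re-dosing that is unrestricted in one section and limited to Part B in another. Because these are patient-safety instructions, and compliance with one section can be a deviation from another, they should be reconciled.

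The remaining exposure is probably small, on the order of the two or so patients not yet in the 31-Jan-2020 table. That rests on the inference that the 58 listed patients had largely finished a four-week course, and on few or no additional Part A enrolments. The effect on how deviations are classified and how Part A safety data are described does not depend on that inference. No endpoint, estimate or test is affected on the evidence visible here.

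**What to change.** Reconcile the synopsis, Section 3.6 and Section 6.9 so that each part has one observation time and one re-dosing rule, stated in the same words in each place where it appears. If the parts are meant to differ, limit the statements in 3.6 and the synopsis to the part they apply to, so that the Part A benefit/risk text rests only on measures applied there. Check that Section 7.2, the stopping rules and Table 8-1 agree with the reconciled text.

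In the study report, describe the Part A hypersensitivity data together with the observation time that was in force when the injections were given.

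Which observation time and which re-dosing rule are right is for the sponsor to decide; this review takes no position.

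The cost is wording in three places at the next amendment and a sentence in the report. The edit itself adds no visits or patients.
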